**5. Specific Aims:**

Aim 1: Assess the impact of treatment with either nabilone or placebo on cannabis use patterns.

Aim 2: Assess the impact of treatment with either nabilone or placebo on performance on neuropsychological testing.

**6. Progress Report and Preliminary Studies:** Not applicable.

**7. Background and Significance:**

Despite the alarming prevalence of cannabis dependence and the corresponding impact upon public health, no consistent pharmacological treatments exist for this disorder. Nabilone (Cesamet®) is a synthetic cannabinoid FDA-approved for cancer chemotherapy with behavioral and physiological effects that overlap with  $\Delta^9$ -THC (Stark and Dews 1980, Mendelson and Mello 1984). Nabilone is safe and well-tolerated, with side effects that diminish with repeated administration (Lemberger et al. 1982). Nabilone’s properties make it an attractive option for study as an agonist treatment, and it may be a better choice than dronabinol for agonist treatment because nabilone is not cross-reactive with urine assays used to detect recent cannabis use (Fraser and Meatherall 1989).

**8. Research and Design Methods:**

**8.1. Overview**

We will conduct a Stage 1 pilot feasibility study at McLean Hospital to develop a medication to treat cannabis dependence. (FIGURE 1) In a randomized, double-blind, placebo-controlled trial, 60 cannabis-dependent subjects ages 18-45 will receive medical management (MM) over a 10-week period, with half receiving nabilone treatment and half receiving placebo. Participants will receive either 6 mg nabilone or placebo in addition to medical management (MM) over a 10-week treatment period.

**McLean Hospital Application to the Institutional Review Board (IRB)  
Nabilone for Cannabis Dependence Detailed Protocol**

Following treatment completion, participants will have a follow-up visits at 11, 12, 13, and 14 weeks. Primary outcomes will include self-report of cannabis smoking and results of quantitative urine drug screens for cannabis. We also will assess craving and other marijuana withdrawal symptoms as secondary measures. Mixed models ANOVA will be used to analyze the data.

The protocol described in this document has been approved by the FDA under IND 107862 to [name].

## **8.2. Participants**

Male and female participants (ages 18-45) will be recruited from the Boston metropolitan area via websites, newspaper advertisements, flyers, and word-of-mouth. In order to meet our target sample of 60 study completers- (participants who complete all study procedures), we expect to recruit about 120 participants and have 90 sign the informed consent form . (Our target sample size is 60 completers with 30 per group: 30 Placebo and 30 Nabilone). From ongoing studies of cannabis smokers at McLean, we expect to recruit at least 3 participants a month for our study.

### **8.2.1. Study Procedure**

#### **8.2.1.a. Recruitment and Intake.**

Interested individuals will respond to advertisements by leaving a message (first name and call back number only) in the BPRL recruiting voice mailbox. Research assistants will call them back with 24 to 48 hours and conduct an initial phone screen that takes about 15 minutes. It will cover basic inclusion and exclusion criteria, as well as a brief description of the study to determine if the person is interested in participating. If the volunteer is appropriate and agrees to participate, they will be invited to come to the BPRL for a physical and psychiatric evaluation (SCID). Treatment alternatives will also be offered to the prospective participant if they decide not to participate or are not eligible for participation.

The initial assessment interview will be done by a research assistant and the study physician and take about 3 hours. Volunteers will first be asked to sign the informed consent (see 8.2.1.b). Once they have agreed to participate, they will undergo a comprehensive evaluation that will include medical, psychiatric, and drug use histories as well as physical, psychiatric, and laboratory examinations. The study will be explained and an intake package, including all Drug and Alcohol and Mood and Impulsivity Assessments (see Table 8.1), will be administered. More specifically, the participants will undergo the following screening procedures:a) Detailed history of cannabis use; b) Review of DSM-IV criteria for cannabis dependence; c) Medical history and concomitant medication record; d) Physical examination; e) Laboratory screen that includes CBC, electrolytes, and BUN/creatinine; f) Urine measurement of THC; g) Urinalysis and urine pregnancy test for women; h) 12-lead electrocardiograph (EKG) i) urine toxicology screen; j) blood alcohol testing; k) Columbia Suicide Severity Rating Scale (C-SSRS). Suicide risk will be assessed by the physician at each MM visit.

**McLean Hospital Application to the Institutional Review Board (IRB)  
Nabilone for Cannabis Dependence Detailed Protocol**

**8.2.1.b. Informed consent.** Eligible participants will complete standard consent documentation. Prior to the volunteer being asked any question about his/her health, the volunteer will be given a consent form to read. The research assistant will go over it in detail with the volunteer. After a physician investigator answers any questions the volunteer may have concerning the study, he/she will be asked to provide their informed consent to the licensed physician investigator. If enrolled in the study, consent to communicate with their other clinicians will be obtained. Clinicians will be notified of their patients' enrollment in the study, thus allowing them to carefully monitor for changes in mood while they are undergoing treatment to stop use of cannabis.

**8.2.1.c. Randomization.** Participants will be stratified according to their self-reported frequency of cannabis use in the past 30 days: 1) daily use; and 2) non-daily use. The stratification procedure will guard against the possibility that one of the experimental conditions (i.e., nabilone or placebo) will be overrepresented by daily users, while non-daily users will predominantly be randomized into the other condition.

**8.2.1.d. Availability and Flow of Subjects into Treatment.** We plan to screen 120 participants in the course of 20 months to achieve our desired sample size.

**8.2.1.e. Study Visits.** Participants will come to the clinic twice a week. One visit will include a medical visit (dispensing of pills and Medical Management; see Sections 8.3.1.b, 8.3.2) and research assessments, including a urine screen (see Section 8.5.2.a and **Table 8.2**). The other visit will consist only of a urine screen (see Section 8.5.2.a). After the 10-week treatment period, participants will have 1 follow-up assessment visit at 14 weeks. During weeks 11, 12, and 13 participants will have 1 weekly Diary/Actiwatch visit to hand in their daily diaries, have their Actiwatch data downloaded, and provide a urine sample.

**8.2.1.f. Clinical Emergencies.** If a participant is intoxicated, the participant will be evaluated medically, sent home in a taxi when safe, and the appointment re-scheduled. If a participant experiences a problem that requires clinical intervention during the course of the study (e.g., mania, suicidal ideation, or dangerous intoxication), we will evaluate the situation medically, make an appropriate recommendation, and help the participant to implement this plan. This could involve hospitalization at McLean, referral to the hospital's outpatient program, or other medical or psychiatric treatment, as clinically appropriate.

[figure not shown]
**8.2.1.g. Participant Payments**

Volunteers will receive a \$50 remuneration for attending the initial assessment interview and an additional \$50 for the baseline visit. They may earn \$25 for each urine sample given on a non-MM day in the first 5 weeks of treatment and then \$30 for each urine sample given on a non-MM day in the last 5 weeks of treatment, and they may earn \$50 for attending the follow-up assessment at 14 weeks. They may earn \$30.00 for each of three Actiwatch /Diary visits at weeks 11, 12, and 13 as well as \$50 for the final follow-up visit. Additionally they may receive a \$40 bonus for attending all follow-up visits and returning the Actiwatch. They may also receive a bonus of up to \$100 for successful

**McLean Hospital Application to the Institutional Review Board (IRB)  
Nabilone for Cannabis Dependence Detailed Protocol**

completion of their diaries. They may earn a total of \$705 for their participation in the study. Medication will be free. In special circumstances, a subject may receive up to \$50 in public transportation cards.

**FIGURE 1. Study Schema**

**8.3. Treatment.**

**8.3.1 Nabilone.**

**8.3.1.a. Rationale for Dose.** Nabilone (Cesamet®, Meda Pharmaceuticals, Somerset, NJ) is a potent synthetic cannabinoid receptor type 1 (CB1) agonist that received FDA approval in 2006 for the treatment of nausea and vomiting associated with cancer chemotherapy (Cesamet® product information). Nabilone will be titrated to 6 mg daily in the nabilone group. Nabilone 2 mg was well-tolerated in the pilot study we recently completed and doses up to 8 mg have been well-tolerated in other patient populations. Recent studies have demonstrated safety of nabilone at doses greater than the 2 mg maximum dose previously covered in IND 107862. [name] group used up to 8 mg

**McLean Hospital Application to the Institutional Review Board (IRB)  
Nabilone for Cannabis Dependence Detailed Protocol**

daily without incident (Haney et al. 2013, Bedi et al. 2013) in cannabis-dependent participants and another group have used up to 3 mg daily in a participants with peripheral neuropathy (Toth et al. 2012, Bestad and Toth 2011). As a result, the FDA has permitted a maximum dose of nabilone 6 mg daily under [name] IND 107862.

**8.3.1.b. Procedures for Dispensing Medication.**

Subjects will be randomized to receive either placebo or nabilone. [name] or the research assistants will present 7 day prescriptions to the McLean pharmacy and the subject will receive blister packs containing 1 week of medication or placebo, separated into daily doses. Subjects will be asked to return unused pills at each weekly medical visit; study staff will then perform a pill count for the study record. All groups will receive capsules following the same schedule: 4 capsules twice daily for 10 weeks. Each capsule will contain either nabilone or placebo, and riboflavin 25 mg (to help assess compliance). Subjects in the nabilone group will take 1 mg of nabilone at bedtime for 1 week, then increase to 1 mg of nabilone twice daily (between 7:00-9:00 a.m. and 9:00-11:00 p.m.) for 1 week, then 2 mg nabilone twice daily for 1 week, then 3 mg nabilone twice daily for 6 weeks before tapering the medication over the final 1 week by taking 2 mg nabilone twice daily for 2 days, then 1 mg twice daily for 2 days, then 1 mg at bedtime for 3 days before stopping. This schedule is designed to maximize the time spent at the maximum dose. Subjects will be assessed for side effects prior to each dosing increase and the study physician will decide if increasing the dose as scheduled is appropriate.

In order to monitor potential side effects from the initial dose of nabilone or dose increases, participants will be observed at the laboratory facility for 3 hours following the following the second dose of the day in weeks 1, 2, 3, and 4. Participants will come into the Behavioral Psychopharmacology Research Laboratory in the evenings for monitoring by a research assistant and a study physician. This observation period is follows the SAMHSA guidelines for induction of buprenorphine, another agonist pharmacotherapy (CSAT 2004). Participants will remain in the natural settings laboratory for 3 hours while having vital signs taken every 30 minutes. Participants will be allowed to leave the facility after being cleared by a study physician. Participants will be allowed to leave the facility if they have 1) pulse rate less than 120 beats per minute; 2) blood pressure less than 140/90.

**8.3.1.c. Dose Adjustment.**

Subjects who cannot tolerate dose increases either subjectively or by monitoring of vital signs (hypotension, for example), will remain at the dose they were taking prior to the increase (4 mg daily, 2 mg daily, or 1 mg daily). Subjects who experience uncomfortable side effects (e.g., drowsiness or vertigo) may have their dose lowered from 6 capsules a day to 4 or from 4 capsules a day to 2; a subject receiving active nabilone, for example, could then have a dose reduction from 6 mg of nabilone daily to 4 mg daily (or lower). None of the subjects in Study 1 required a dose reduction. If this leads to fewer side effects, the study physician will ask if the subject is willing to try the full dose again. If not, or if the subject tries the full dose again and is unable to tolerate

**McLean Hospital Application to the Institutional Review Board (IRB)  
Nabilone for Cannabis Dependence Detailed Protocol**

it, the subject will be maintained on the lower dose. If a subject cannot tolerate 2 capsules per day, the medication will be discontinued, but the subject will continue to be followed for research visits.

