**8.4. Safety Monitoring.** Nabilone has been shown to have a favorable safety profile; it has been well-tolerated in several clinical trials and no adverse events have been reported (Ware et al. 2008, Frank et al. 2008, Skrabek et al. 2008). Drug-drug interactions are not a major concern with nabilone because it does not induce cytochrome P450 3A4 isoenzymes and lacks significant 3A4 inhibitory effect (Nahas et al. 2002). Nonetheless, we will monitor safety through the standardized methods described above in the MM visits. We will have a low threshold for obtaining additional medical workup during the study if the subject reports medical symptoms. If a participant has a clinically significant laboratory or other medical abnormality that cannot be attributed to another cause, the participant's medication will be discontinued and the participant will be followed for research visits.

**McLean Hospital Application to the Institutional Review Board (IRB)  
Nabilone for Cannabis Dependence Detailed Protocol**

As discussed above in Section 8.2.i.a, the study physician will perform a physical examination and obtain an ECG at baseline and at 14 weeks. Laboratory data (urinalysis, blood chemistries, complete blood count, electrolytes, and liver function tests) will be done at baseline and at 14 weeks as well. Given that according to its labeling, nabilone should not be taken with alcohol, sedatives, hypnotics, or other psychoactive substances because they could potentiate the central nervous system effects of nabilone, urine toxicology and blood alcohol testing will be done weekly along with the twice weekly quantitative THC urine screens during treatment. Women of childbearing potential will have urine pregnancy tests weekly each time a urine sample is given in addition to pregnancy tests at weeks at 4, 10, and 14 weeks during treatment; women who become pregnant will have their medication discontinued and will be referred to an obstetrician; like all participants, they will still be followed for research visits.

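### Section 8.3.1.c leaves two unreconciled rules (hold at 1 mg or discontinue) for a participant who does not tolerate 2 mg daily, and its capsule counts do not fit Section 8.3.1.b

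*Combined protocol and SAP*

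**What the plan says.** Section 8.3.1.b sets the titration. A participant on nabilone "will take 1 mg of nabilone at bedtime for 1 week, then increase to 1 mg of nabilone twice daily", and "then 2 mg nabilone twice daily for 1 week, then 3 mg nabilone twice daily for 6 weeks", before a one-week taper. The same section has every group take four capsules at each of two daily doses for all 10 weeks, each capsule holding either nabilone or placebo. It does not give the mg per capsule.

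Section 8.3.1.c then gives two rules.

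- **Hold rule.** It opens with "Subjects who cannot tolerate dose increases either subjectively or by monitoring of vital signs (hypotension, for example" and says that these participants "will remain at the dose they were taking prior to the increase (4 mg daily, 2 mg daily, or 1 mg daily".
- **Lowering sequence and stop rule.** Participants with uncomfortable side effects "may have their dose lowered from 6 capsules a day to 4 or from 4 capsules a day to 2". Someone on active drug "could then have a dose reduction from 6 mg of nabilone daily to 4 mg daily (or lower". After an offer to retry the full dose, the section closes with "If a subject cannot tolerate 2 capsules per day, the medication will be discontinued", and research follow-up continues.

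Section 8.4 separately stops medication for a "clinically significant laboratory or other medical abnormality that cannot be attributed to another cause".

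**The concern.** Both the hold rule and the stop rule are written as firm instructions, and neither refers to the other. A participant who reaches 2 mg daily in week 2 and cannot tolerate it appears to meet both. One keeps the participant on drug at 1 mg; the other ends treatment.

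Whether someone who has just shown intolerance goes on receiving drug should not depend on which sentence a physician reads. The choice also decides whether that person is recorded as having stopped medication, which is useful information in a study that calls itself a pilot of feasibility with 30 completers planned per group (Section 8.2).

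**Working it through.** **1. The ladder.** From Section 8.3.1.b: 1 × 1 = 1 mg, 2 × 1 = 2 mg, 2 × 2 = 4 mg, 2 × 3 = 6 mg daily. The doses held before the three increases are therefore 1, 2 and 4 mg, which reproduces the list in Section 8.3.1.c exactly. Each hold level belongs to one failed step: 4 mg to the step 4→6, 2 mg to 2→4, and 1 mg to 1→2. The 1 mg level has no other use within the hold rule.

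**2. The dose behind the stop rule.** The stop rule is in capsules, so a strength is needed. None is stated. Three readings are possible:

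| Reading | mg per capsule | 2 capsules a day | Result |
|---|---|---|---|
| Extend the example in 8.3.1.c | 6/6 = 4/4 = 1 | 2 × 1 = 2 mg | Failing 1→2 mg meets both the hold and the stop rule |
| The 8 capsules of 8.3.1.b carry 6 mg evenly | 6/8 = 0.75 | 2 × 0.75 = 1.5 mg | Not a scheduled dose; 6 and 4 capsules would be 4.5 and 3.0 mg, against the 6 and 4 mg in 8.3.1.c |
| Always 8 capsules, with 1 mg active capsules made up by placebo | mixed | 0, 1 or 2 mg, by mix | Count does not identify dose |

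On the third reading the active and placebo counts at 1, 2, 4 and 6 mg are 1 + 7, 2 + 6, 4 + 4 and 6 + 2. The participant takes 8 capsules at every level, so moves from 6 to 4 to 2 capsules describe nothing in the dispensing schedule.

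**3. The two rules side by side, on the first reading.**

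- Intolerance of 2 mg on the way up: the hold rule gives 1 mg daily; the stop rule, which is not limited to any phase, gives discontinuation.
- Intolerance of 2 mg after lowering from 6 or 4 mg: the stop rule gives discontinuation.

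If the stop rule governs throughout, the listed 1 mg hold level is never reached. If it governs only after lowering, intolerance of the same dose has different consequences according to the route by which it was reached, and the protocol neither states nor explains that.

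**4. The boundary with Section 8.4.** Hypotension on an increase is an example under the hold rule. Section 8.4 names neither vital signs nor dose increases. The two overlap only if a vital-sign change is judged a clinically significant abnormality with no other cause, and the text does not say whether the study drug is itself a cause to be excluded. The only numerical vital-sign limits, in Section 8.3.1.b, are upper limits on pulse and blood pressure for leaving the laboratory. They do not mark the line between holding and stopping.

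**The case against.** The best defence is to read Section 8.3.1.c in order. The first sentence deals with failed increases; the later ones form a separate path of lowering, retrying, maintaining and, at the end, stopping. On that reading the stop rule closes only the lowering path and the 1 mg hold level stays in use. This is a fair reading, and it is why one cannot say that the section plainly gives opposite instructions or that the 1 mg level can never apply. But the limit is not written, and the stop sentence carries no condition.

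The second defence is that 2 capsules equalling 2 mg is an inference. That stands. With placebo in the mix, two capsules could carry 1 mg, and the conflict would disappear. The documents do not settle it, and this reading leaves the stop rule without a defined dose, which is a defect of its own.

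Third, there are safeguards. Under Section 8.3.1.b the physician assesses side effects before each increase and decides whether to proceed, with three hours of observation in each of weeks 1 to 4. Both rules move away from the dose that was not tolerated. These points lower the stakes, but they do not say what happens after an increase has failed.

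A reader might also infer that Section 8.4 adds a third conflicting rule for vital-sign events. It does not. It contains no such rule, its action is the same as that of the stop rule, and it can be read as a more serious tier left to judgement. What remains is an undefined boundary.

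**Conclusion.** The point holds as an unreconciled inconsistency in wording that bears on participant safety. Section 8.3.1.c does not say how its hold and stop rules fit together for intolerance of 2 mg daily, and the 8 capsules a day of Section 8.3.1.b do not match its steps of 6, 4 and 2. The first part rests on extending the 1 mg per capsule implied by the section's own example. The capsule mismatch needs no such assumption.

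Its size cannot be put as a number of participants. A reader might assume a rate of intolerance and multiply by 30, but the documents give no rate. What evidence they offer points to few cases: Section 8.3.1.a reports that 2 mg was well tolerated in the completed pilot, and Section 8.3.1.c reports no dose reductions in a Study 1 that it does not define.

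Nor does it follow that a main result is at risk. Stopping for intolerance is not a named outcome. Participants taken off medication remain in follow-up, and the primary analysis in Section 8.9 includes everyone randomized. No primary analysis figure changes. No figure in the documents supports a claim that the ambiguity falls more heavily on the active arm.

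**What to change.** Reconcile Sections 8.3.1.b and 8.3.1.c into one dose-adjustment rule:

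- Express every level in mg per day, with the blinded placebo equivalent, and state the capsule strength and the active and placebo make-up of each daily dose.
- Say whether the stop rule applies to failed increases, to dose lowering, or to both, and hence whether 1 mg daily is a permitted maintenance level.
- In the same edit, say when an event on a dose increase falls under the hold rule of Section 8.3.1.c and when under the discontinuation rule of Section 8.4.

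The clinical content of each choice is for the sponsor; nothing here favours one dose or rule over another. The cost is a protocol wording amendment, with no added visits, data or analyses.

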**8.3.2. Medical Management Visits.**

**8.3.2.a. Weekly Visits with the Study Physician.** Participants will be seen weekly during treatment by the study physician for medical visits. In addition to dispensing the study medication, the physician will utilize Medical Management (MM) (Pettinati et al 2004), a manualized treatment that was used in the NIAAA COMBINE Study. MM was derived from empirically-tested manualized therapies (Carroll and O'Malley 1996, Mason and Goodman 1997) that were originally designed to approximate a primary care approach to the treatment of alcohol dependence. The treatment is delivered by a medical professional who monitors medication side effects, provides strategies to increase medication adherence (Volpicelli et al. 1997), and supports abstinence. The initial 40-60 minute session includes reviewing the cannabis dependence diagnosis and negative consequences from smoking marijuana, recommending abstinence, providing medication information, and offering strategies to enhance medication adherence. In subsequent 15-25 minute visits, recent substance use, overall functioning, medication adherence, and side effects are discussed. Session structure varies according to drug use status and medication adherence. If a participant is not adherent to the medication regimen, the clinician evaluates the reasons and helps the subject devise plans to enhance medication adherence. Participants who use cannabis are given common-sense behavioral recommendations, such as avoiding parties where marijuana will be present. Presence and severity of side effects will be obtained through a standard Adverse Events Checklist as well as the "Frequency and Intensity of Side Effects Rating/Global Report of Side Effects Burden" (Wisniewski et al. 1997), a 2-minute questionnaire that assesses the frequency, intensity, and level of burden of side effects. Medication adherence will be assessed in several ways, as outlined below in Section 8.6. These sessions will be audiotaped and a sample will be rated by a senior clinician in order to ensure fidelity to the MM process.

**8.4. Safety Monitoring.** Nabilone has been shown to have a favorable safety profile; it has been well-tolerated in several clinical trials and no adverse events have been reported (Ware et al. 2008, Frank et al. 2008, Skrabek et al. 2008). Drug-drug interactions are not a major concern with nabilone because it does not induce cytochrome P450 3A4 isoenzymes and lacks significant 3A4 inhibitory effect (Nahas et al. 2002). Nonetheless, we will monitor safety through the standardized methods described above in the MM visits. We will have a low threshold for obtaining additional medical workup during the study if the subject reports medical symptoms. If a participant has a clinically significant laboratory or other medical abnormality that cannot be attributed to another cause, the participant's medication will be discontinued and the participant will be followed for research visits.

**McLean Hospital Application to the Institutional Review Board (IRB)  
Nabilone for Cannabis Dependence Detailed Protocol**

As discussed above in Section 8.2.i.a, the study physician will perform a physical examination and obtain an ECG at baseline and at 14 weeks. Laboratory data (urinalysis, blood chemistries, complete blood count, electrolytes, and liver function tests) will be done at baseline and at 14 weeks as well. Given that according to its labeling, nabilone should not be taken with alcohol, sedatives, hypnotics, or other psychoactive substances because they could potentiate the central nervous system effects of nabilone, urine toxicology and blood alcohol testing will be done weekly along with the twice weekly quantitative THC urine screens during treatment. Women of childbearing potential will have urine pregnancy tests weekly each time a urine sample is given in addition to pregnancy tests at weeks at 4, 10, and 14 weeks during treatment; women who become pregnant will have their medication discontinued and will be referred to an obstetrician; like all participants, they will still be followed for research visits.

